2.8.2 Deaths

A separate summary of deaths including on-treatment and post-treatment deaths will be provided.

All deaths in the clinical database will be listed with the investigator-reported principal cause. Deaths occurring after the first dose of study treatment until 30 days after the date of last treatment will be summarized. In addition, deaths occurring after the first dose of study treatment and before the date of last treatment will be summarized.

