12.5.2 Analysis of secondary safety endpoints

For all safety analyses, the Safety Set will be used. All listings and tables will be presented by treatment group.

Safety summaries (tables, figures) will include only data from the on-treatment period with the exception of Baseline data, which will also be summarized where appropriate (e.g. change from Baseline summaries). In addition, a separate summary for death including on-treatment and post-treatment deaths will be provided. In particular, summary tables for AEs will summarize only on-treatment events, with a start date during the on-treatment period (i.e. treatment-emergent AEs as defined below).

The on-treatment period lasts from the date of first administration of study treatment to 30 days after the date of the last actual administration of any study treatment.

Adverse events

All information obtained on AEs will be displayed by treatment group and patient.

The number (and percentage) of patients with treatment-emergent AEs (defined as events started after the first dose of study medication or events present prior to start of study treatment but increased in severity based on PT) will be summarized in the following ways:

- By treatment, primary system organ class and PT.
- By treatment, primary system organ class, PT and maximum severity.
- By treatment, standardized MedDRA query and PT.

Separate summaries will be provided for study medication related AEs, death, SAEs, other significant AEs leading to discontinuation, AEs leading to dose adjustment and AE of special interest.

Adverse events will be summarized by presenting, for each treatment group, the number and percentage of patients having any AE, having an AE in each primary system organ class and having each individual AE (PT). Summaries will also be presented for AEs by severity and for study treatment related AEs. If a patient reported more than one AE with the same PT, the AE with the greatest severity will be presented. If a patient reported more than one AE within the same primary system organ class, the patient will be counted only once with the greatest severity at the system organ class level, where applicable. Serious adverse events will also be summarized.

Vital signs

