- Achieves ASDAS clinically important improvement (i.e. responder) will continue with secukinumab 300 mg s.c. every 4 weeks up to Week 32.
- Do not achieve ASDAS clinically important improvement (i.e. non-responder), will be switched to adalimumab biosimilar (GP2017) 40 mg s.c. every 2 weeks until Week 34.

Escape arm

- Subjects who are receiving 150 mg secukinumab (i.e. were responders at Week 12) can be escalated at Week 24 to 300 mg secukinumab every 4 weeks until Week 32 if they experience a loss of response, where loss of response is defined as ASDAS change from Baseline <1.1 .

If the ASDAS measurement is missing at a visit, it is assumed that the planned dose continues for the next treatment period.

Standard of Care Regimen

Patients will receive treatment according to local practice standards by their treating physician following the current treatment recommendations with NSAIDs as the first-choice drug treatment and disease-modifying anti-rheumatic drugs (DMARDs) for patients with active disease because of a lack of response, intolerance, or contraindication to NSAIDs ([van der Heijde et al 2017](#)). Patients will be seen every 12 weeks or more often, if clinically indicated up to Week 36; assessment of the outcome parameters will be performed at Week 12, Week 24 and Week 36.

Study treatment (T2T) start and end date: Study treatment start date is defined as the first date of study drug administration and recorded on the Drug Administration Record (DAR) Electronic Case Report Form (eCRF) page. Similarly, study drug end date is defined as the last date of study drug administration and is recorded on the DAR eCRF page.

SOC treatment start and end date: SOC treatment start date is defined as the first date of any SOC drug for AxSPA treatment after randomization. Similarly, SOC drug end date is inferred as the last date of any SOC drug administration for AxSPA treatment within the treatment phase.

Study day: Study Day 1 is defined as the first day of administration of randomized study treatment. Study day will be calculated as (event date – study drug start date + 1 day) for events that occurred on or after study drug start date (e.g. visit, lab samples, AEs). For events prior to study drug start date (e.g. time since diagnosis), study day will be negative and calculated as (event date – study drug start date).

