Baseline and post-Baseline: Baseline value refers to the value of the last non-missing measurement collected prior to administration of the first dose of study treatment (screening or Baseline visit). A post-Baseline value refers to a measurement taken after the first dose of study treatment.

Change from Baseline: The difference of measure between post-Baseline and Baseline is called change from Baseline.

Percent change from Baseline: The percent change from Baseline will be calculated as below:
 $((\text{post-Baseline value} - \text{Baseline value}) / \text{Baseline value}) * 100$.

On-treatment period: The on-treatment period lasts from the date of first administration of study treatment to 30 days after the date of the last actual administration of any study treatment or end of treatment phase, whichever is later.

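### SAP 2.8.2 plans a summary of deaths that can contain no death, and its 30-day death window differs from the on-treatment period used for the AE tables

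*SAP*

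**What the plan says.** SAP 2.8.2 plans four outputs on deaths:

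- an overall summary: "A separate summary of deaths including on-treatment and post-treatment deaths will be provided". This carries over the commitment in protocol 12.5.2 that "a separate summary for death including on-treatment and post-treatment deaths will be provided";
- a listing of every death in the clinical database, with cause;
- a 30-day window: "Deaths occurring after the first dose of study treatment until 30 days after the date of last treatment will be summarized";
- a narrower window: "deaths occurring after the first dose of study treatment and before the date of last treatment will be summarized".

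The date of last treatment is not defined as a term. The nearest definitions are in SAP 2.1.1. For T2T, "study drug end date is defined as the last date of study drug administration". For standard of care, "SOC drug end date is inferred as the last date of any SOC drug administration for AxSPA treatment within the treatment phase".

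SAP 2.1.1 ends the on-treatment period at "30 days after the date of the last actual administration of any study treatment or end of treatment phase, whichever is later". SAP 2.8.1 restricts the AE tables to events that start within that period, and also asks for counts of deaths resulting from SAEs. Protocol 12.5.2 has no extension to the end of the treatment phase: "The on-treatment period lasts from the date of first administration of study treatment to 30 days after the date of the last actual administration". SAP Section 4 records no change to the protocol's analyses.

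**The concern.** A summary of deaths up to the last treatment looks like a count of deaths while on drug. As worded, it cannot count one. A patient who dies halfway between two injections had the last dose before death, so the death is after the date of last treatment and the row stays at zero.

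The second issue is that one idea, on-treatment, has two boundaries in the same safety section. Deaths should be few, so the classification of a single one can change the table. A reader who compares the AE tables with the death summary may find a fatal event that is on-treatment in one and absent from the other, with nothing to explain it.

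**Working it through.** The plan states no figure on this point to reproduce; the check is date logic.

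**Inputs.** Scheduled day = 7 × week + 1, which agrees with SAP Table 2-1 (Week 12 = Day 85, Week 24 = Day 169, Week 36 = Day 253). Planned last doses are Week 32 (Day 225) for secukinumab and Week 34 (Day 239) for adalimumab (protocol 6.1.3). The treatment phase ends the day before the Week 36 visit. If no further visit takes place, it ends at the documented end-of-treatment date, or at the period's start date if nothing was given in that period (SAP 2.1.1). Patients who stop drug may stay in the study (protocol 6.5).

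**Step 1: the narrower window.** Let L be the day of last administration and D the day of death. Nobody is dosed after death, so L ≤ D. The window requires D < L. Both cannot hold. Enumerating death days 1 to 399 with every L up to D gives 0 qualifying pairs. A death on the day of the last dose is also excluded, because D < L is strict.

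The row could fill only if the recorded L is wrong or imputed. SAP 5.1.1 (Scenario 2, Case 1) replaces a wholly missing dose end date with the end-of-treatment completion date, which could fall after death.

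**Step 2: the 30-day window against SAP 2.1.1.** The death window ends at L + 30. With P as the end of the treatment phase, the SAP 2.1.1 sentence can be read in two ways:

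- Reading A: max(L + 30, P)
- Reading B: max(L, P) + 30

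| Patient | L | P | Death window ends | A ends (gap) | B ends (gap) |
|---|---|---|---|---|---|
| Secukinumab completer, on schedule | 225 | 252 | 255 | 255 (0) | 282 (27) |
| Same, Week 36 visit 7 days late | 225 | 259 | 255 | 259 (4) | 289 (34) |
| Adalimumab completer | 239 | 252 | 269 | 269 (0) | 282 (13) |
| Last dose Week 20, attends Weeks 24 and 36 | 141 | 252 | 171 | 252 (81) | 282 (111) |
| Last dose Week 8, attends Weeks 12, 24 and 36 | 57 | 252 | 87 | 252 (165) | 282 (195) |
| Last dose Week 8, attends Weeks 12 and 24 only | 57 | 169 | 87 | 169 (82) | 199 (112) |

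In the rows where Week 36 is attended, any death comes after that visit, so under reading A the gap concerns AE onset dates and not death dates.

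**Step 3: a case that can occur.** Take the last row, with a fatal AE starting on Day 141 and death on Day 183. No dose was given in period 3, so P = 169.

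- AE tables: 141 ≤ 169, so the AE is on-treatment.
- 30-day death summary: 183 > 57 + 30 = 87, so the death is not counted.

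**Step 4: would one boundary remove this?** Under reading A for both tables, the AE is in (141 ≤ 169) and the death is out (183 > 169). Under reading B, both are in (183 ≤ 199). Under the protocol rule of last dose + 30 days, both are out (141 and 183 exceed 87). No boundary removes every split: under the protocol rule, an onset on Day 80 with death on Day 95 still straddles Day 87. AE tables go by onset date and death tables by death date.

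**The case against.** The strongest reply is that the harm is small. A patient who dies between two injections still appears in the 30-day summary, the overall summary and the listing. The empty row is redundant and hides nobody. That stands, and it limits the point to a faulty output, with no missing deaths.

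It can also be said that the 30-day window is not the odd one out. It follows protocol 12.5.2, and last dose + 30 days is also the rule for laboratory data (SAP 2.8.3) and on-treatment exposure (SAP 2.4.1). SAP 2.1.1 is the exception. That stands too: moving deaths to the 2.1.1 period is not self-evidently the right repair.

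Three stronger readings are tempting, and the documents do not support them:

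- A reader might subtract Day 87 from Day 252 for a Week 8 stopper and infer that for 165 days a death is on-treatment in one table and not in the other. A patient who dies in that interval never attends Week 36, and SAP 2.1.1 then sets an earlier phase end. Under reading A the death date itself will rarely fall between the limits; the mismatch arises mainly through AE onset.
- A reader might infer that the tables will disagree. They can, but only if a fatal event falls between the limits. Under reading A the limits coincide for on-schedule T2T completers.
- A reader might infer that deaths beyond day 30 go uncounted. The overall summary covers post-treatment deaths and the listing covers all. What is missing is a stated split between on- and post-treatment.

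**Conclusion.** The narrower death summary is wrong as written. If the date of last treatment means last administration, as the SAP's end dates do, its count is 0 in both arms whatever happens, barring imputed or mis-recorded end dates.

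The 30-day death window and the SAP 2.1.1 on-treatment period are different rules. In the cases worked, their ends differ by 0 to 165 days under one reading of 2.1.1 and by 13 to 195 days under the other, with the largest gaps for patients who stop early and stay in follow-up. A fatal AE can therefore be on-treatment while the death is outside the 30-day summary. How often this would happen cannot be derived from the documents. No death is lost and no efficacy result is affected.

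**What to change.** In SAP 2.8.2:

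- Delete the summary of deaths before the date of last treatment.
- Define the date of last treatment for each arm, including what applies when the end date is imputed under SAP 5.1.1.
- Use one stated on-treatment boundary for the death and AE tables. This means reconciling SAP 2.1.1 with protocol 12.5.2; the documents do not settle which should govern. If the 2.1.1 period is kept, state which reading of its end applies and record the departure from the protocol in SAP Section 4. Align or explain the 30-day rules in SAP 2.4.1 and 2.8.3 as well.
- Tabulate by arm the on-treatment deaths, the post-treatment deaths (to Week 56 or last contact) and all deaths.
- Add a footnote that AE tables classify by onset date and death tables by death date, so a single event may be placed differently.

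The cost is SAP wording and one table shell. No data collection or trial procedure changes.

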2.8.3 Laboratory data

All laboratory data will be listed with abnormal values flagged.

Laboratory data measured more than 30 days after the last dose of study drug is regarded as post-treatment and will not be summarized or analyzed, only listed.

The below laboratory parameter data will be analyzed.

Hematology: Hemoglobin, hematocrit, platelet count, red blood cell, WBC and differential WBC counts.

Clinical chemistry: glucose, urea, creatinine, total bilirubin, AST, ALT, gamma-glutamyl transferase (GGT), alkaline phosphatase, sodium, potassium, bicarbonate, calcium, phosphorous, total protein, albumin, and uric acid.

Lipid panel: High density lipoprotein, low density lipoprotein, cholesterol and triglycerides must be measured from a fasting blood sample.

Urinalysis: Protein, glucose, blood and WBCs.

For all continuous laboratory parameters, summary statistics for absolute and change from Baseline values will be provided at each visit. All laboratory data (including any unscheduled assessments) will be listed with abnormal values flagged.

For categorical urinalysis laboratory parameters (Glucose, Occult Blood, Protein), a frequency table of results will be produced by laboratory parameter, scheduled visit and treatment.

Shift tables for laboratory parameters will be provided in order to compare a subject's Baseline value to the value at each study visit, relative to the normal reference range for each lab parameter. Abnormal values marked in Section 5.4 will be used to evaluate whether a particular laboratory test value for each visit is normal, low or high relative to the Baseline value also categorized as normal, low or high. These summaries will be presented by laboratory parameter, visit and treatment group.

In addition, shift tables relative to the normal reference ranges will be used to summarize the change from Baseline to the most extreme post-Baseline for each laboratory parameter. For each laboratory test, the subjects will be classified into one of the four mutually exclusive groups (low, normal, high, and low + high), defined as follows:

- Low: at least one post-Baseline value below the normal range and none above the normal range
- High: at least one post-Baseline value above the normal range and none below the normal range
- Normal: all the post-Baseline values within the normal range
- Low + High: at least one post-Baseline value below the normal range and at least one above the normal range

Categorical parameters in the urinalysis panel will also be summarized with shift tables showing the shift from one categorical result to another.

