6.1.3 Treatment duration

Each patient will be treated for a maximum of 36 weeks (last dose of secukinumab at Week 32, last dose of adalimumab biosimilar (Hyrimoz®) at Week 34).

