6.6 Additional treatment guidance

6.6.1 Treatment compliance

All dates of study treatment and reference treatment administration will be recorded on the appropriate CRF.

Drugs administered prior to start of treatment and other drugs/procedures continued or started during the study treatment/reference treatment period will be entered in the appropriate CRF.

Compliance to study treatment and reference treatment is expected to be 100% if possible, unless temporary interruption is needed for safety reasons as described in [Section 6.5](#). In case full compliance with the visit schedule for the T2T arm cannot be reached, visits and/or treatments that fall into the following tolerance levels do not constitute a PD:

V1 up to and including V4: +/- 2 days

V5: +/- 3 days

V6 up to and including V9: +/- 7 days

V10 up to and including V15 for patients treated with secukinumab: +/- 7 days

V10 up to and including V15 for patients treated with adalimumab: +/- 3 days

Compliance will be assessed continuously during the conduct of the study by Novartis study personnel using medication kits and corresponding documentation.

Study drug doses and corresponding dates of self-administration at home should be documented in a self-administration log. Patients are required to return the self-administration log as well as all dispensed study drug for a compliance check at their subsequent visit back to the study center. Compliance will be assessed by a field monitor using information provided by the patient and the authorized site personnel. All study treatment dispensed and returned must be recorded in the Drug Accountability Log.

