2.1.1 General definitions

Study treatment: Study treatment refers to:

1. Investigational treatment Treat to Target (T2T) = secukinumab 150 mg and/or 300 mg and/or adalimumab biosimilar 40 mg (GP2017)
2. Standard of Care (SOC) treatment up to the maximum recommended dose at the discretion of the investigator

The **treatment phase** is defined as the period from randomization until end of the last treatment period with treatment periods defined as:

- Period 1: date of randomization until day before visit Week 12
- Period 2: date of visit Week 12 until day before visit Week 24

- Period 3: date of visit Week 24 until day before visit Week 36

The following exceptions are made to these definitions:

- If visit Week 12 or 24 is missing but the next visit is documented, the visit date is interpolated in the middle between the earlier and the later visit.
- End dates of period 1, 2, 3: If no further visit was performed during the treatment phase after start of the period, the end date is set to the documented end of treatment date or to the period start date, if no treatment was applied in this period.
- End date of period 3: If the documented end of treatment date is on visit Week 36 date or later, the end date of period 3 is set to the end of treatment date.
- Treat-to-Target group: If treatment was not applied at visit Week 12 or 24, or the last dose of the previous period was still applied on the date of visit, the start date of period 2 resp. 3 is set to the date of first dose in this period. Cases where the last dose of the previous period was still applied on the visit date are identified by the same dose as in the previous period applied on the visit date, but treatment was switched at the first dose after the visit.

Treat-to-Target regimen

Starting from Baseline, subject will be treated with secukinumab 150 mg subcutaneous (s.c.) weekly until Week 4 and then at Week 8.

At Week 12

- If the subject achieves and maintains an ASDAS clinically important improvement (i.e. change from Baseline in ASDAS ≥ 1.1 indicating subjects is a responder), then the subject will continue with secukinumab 150 mg s.c. every 4 weeks up to Week 32.
- If the subject did not achieve ASDAS clinically important improvement (i.e. non-responder) then the subject will receive an escalated dose of secukinumab 300 mg s.c. every 4 weeks until Week 20.

At Week 24

Subjects who are receiving secukinumab 300 mg and

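### SAP 2.8.3 leaves 2 days of slack for Week 36 laboratory values in secukinumab patients where the protocol tolerates 7, so late but compliant samples are listed only

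*SAP*

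**What the plan says.** - **Laboratory rule (SAP 2.8.3).** "Laboratory data measured more than 30 days after the last dose of study drug is regarded as post-treatment and will not be summarized". The values remain visible, because "All laboratory data will be listed with abnormal values flagged".
- **Last planned dose (Protocol 6.1.3).** "last dose of secukinumab at Week 32, last dose of adalimumab biosimilar (Hyrimoz®) at Week 34".
- **Tolerances (Protocol 6.6.1).** In the T2T arm, "visits and/or treatments that fall into the following tolerance levels do not constitute a PD". The limits that matter here are "V10 up to and including V15 for patients treated with secukinumab: +/- 7 days" and "V10 up to and including V15 for patients treated with adalimumab: +/- 3 days". V13 is Week 32, V14 is Week 34 and V15 is Week 36.
- **On-treatment period.** Protocol 12.5.2 restricts safety summaries to on-treatment data and ends that period 30 days after the last administration. SAP 2.1.1 ends it later, at "30 days after the date of the last actual administration of any study treatment or end of treatment phase, whichever is later". SAP 2.8.3 does not carry the added clause.
- **End of the treatment phase (SAP 2.1.1).** "Period 3: date of visit Week 24 until day before visit Week 36". The exception is a documented end-of-treatment date on or after the Week 36 visit, which then becomes the end.
- **Week 36 analysis window (SAP Table 2-1).** Scheduled Day 253, window Day 212 to Day 364.

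**The concern.** Week 36 is an analysis visit, and SAP 2.8.3 promises laboratory summaries at each visit. The 30-day cut-off does not match the visit tolerance or the Week 36 window. A secukinumab patient can comply fully with the protocol and still have the Week 36 result left out of the tables.

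The loss depends on drug and punctuality. It arises for drugs with long dosing intervals, which in the T2T arm means secukinumab, and showing the safety and tolerability of secukinumab is a stated objective. An abnormality first seen in a late Week 36 sample would appear in a listing but not in the by-visit, change-from-Baseline or shift tables. SAP 2.8.4.2 states no such cut for vital signs, so on the SAP's text the same patient's Week 36 blood pressure would be summarised while the laboratory result from the same day would not.

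**Working it through.** **1. Reproduce the plan's calendar.** Scheduled day = 7 × week + 1. Weeks 12, 24 and 36 give Days 85, 169 and 253, as in SAP Table 2-1. The last secukinumab dose (Week 32) is then Day 225 and the last adalimumab dose (Week 34) is Day 239.

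**2. Nominal gap from last dose to Week 36.**
- Secukinumab: 253 − 225 = 28 days. The last day kept is 225 + 30 = Day 255, so the slack is 2 days.
- Adalimumab: 253 − 239 = 14 days.

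**3. Gap within tolerance.** Gap = nominal gap + visit shift − dose shift.
- Secukinumab, dose on Day 225, visit ± 7: 21 to 35 days. Visits 3 to 7 days late exceed 30, which is 5 of 15 possible days (33%).
- Secukinumab, dose and visit both ± 7: 14 to 42 days. The rule bites when visit shift − dose shift ≥ 3. A difference of k days arises in 15 − k ways, so the count is 12 + 11 + … + 1 = 78 of 15 × 15 = 225 pairs (35%).
- Adalimumab, both ± 3: 8 to 20 days, never excluded.

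**4. Share of secukinumab patients affected.** The documents do not give the spread of dates, so these are assumptions. Dose and visit shifts are taken as independent and limited to ± 7 days.

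| Assumed spread | Gap over 30 days |
|---|---|
| Normal, SD 1 day, both dates | about 4% |
| Normal, SD 2 days, both dates | about 19% |
| Normal, SD 3 days, both dates | about 27% |
| All days equally likely, both dates | 35% |

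**5. Does another definition rescue these values?** The extended on-treatment period in SAP 2.1.1 would not, even if 2.8.3 adopted it. The treatment phase normally ends the day before the Week 36 visit, so a sample taken at that visit 31 or more days after the dose misses by one day. Only the documented end-of-treatment exception would bring it in. The analysis window does not help either: with the last dose on Day 225, Days 256 to 364 (109 of the window's 153 days) lie past the cut-off.

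**6. SOC arm.** SAP 2.1.1 takes the SOC end date as the last SOC drug date within the treatment phase. A patient on continuing medication has a gap near zero.

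**7. What cut-off would suffice?** At 35 days every compliant sample is kept if the dose was on Day 225, but 7 + 6 + … + 1 = 28 of 225 pairs (12%) are still lost when both dates move. At 42 days none is lost.

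**The case against.** - **SAP 2.8.3 follows the protocol.** Protocol 12.5.2 sets the 30-day on-treatment limit for safety summaries, and the text that departs from it is SAP 2.1.1. This stands. The fix is therefore a change to a protocol-specified analysis and has to be declared as one. It does not remove the mismatch, because the protocol's own 30-day limit and 7-day tolerances produce it.
- **A reader might infer that on-schedule Week 36 T2T results are discarded.** The documents do not support that. A sample on Day 253 is 28 days after the dose and is kept, patients switched to adalimumab are never caught, and excluded values are still listed and flagged.
- **A reader might infer that the whole SOC arm is kept while T2T loses data.** This holds only for SOC patients on continuing medication. Those who stop, or who receive an injected biologic at long intervals, can also pass 30 days.
- **The size is assumed.** Protocol 6.6.1 expects full compliance where possible, so 35% is an upper illustration. If a late dose pushes the visit back as well, the share falls. This stands.
- **The consequence is limited.** These are descriptive tables. Earlier on-treatment values still enter the most-extreme-value shift tables, and no efficacy analysis is touched. This also stands.
- **Summarising every Week 36 value regardless of time since last dose would be too broad.** Patients who stop treatment remain in the study (Protocol 6.5 and 9.1.1), and their off-drug values would enter on-treatment tables. This stands and limits the fix.

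**Conclusion.** The mismatch is real but narrow. For T2T patients still on secukinumab, Week 36 laboratory values taken 31 to 42 days after the last dose can be fully protocol-compliant and yet appear only in listings. The day arithmetic rests on the documents, with tolerances read as measured from the nominal day. The share affected is unknown: about 4% to 35%, depending on the assumed spread and on independent dose and visit shifts. Week 36 laboratory sampling is itself inferred, because the laboratory rows of Table 8-1 are missing from the text available; Protocol section 3 places safety evaluations in the regular visits up to Week 36, and Protocol 8.4.4.1 places haematology at scheduled visits. The primary analysis is unaffected. The plan should still be corrected, because the omission is selective by drug and visit timing and is cheap to remove.

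**What to change.** In SAP 2.8.3, count scheduled Week 36 laboratory values as on-treatment up to 42 days after the last dose. An alternative is to count them up to and including the Week 36 visit for patients who received the last planned dose. Flag values taken more than 30 days after the last dose, so that the tables can be repeated without them.

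For patients who stopped treatment earlier, leave the 30-day limit in place so that their off-treatment values stay out of the on-treatment tables. A patient who missed only the Week 32 dose has a nominal gap of 253 − 197 = 56 days (last dose at Week 28, Day 197) and would still be listed only; the SAP should say so.

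Reconcile the on-treatment definitions in Protocol 12.5.2 and SAP 2.1.1 with this rule, and record the change in SAP section 4, which now reports no changes to protocol-specified analyses.

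The cost is SAP wording, one programming flag and a declared departure from the protocol's 30-day rule. Some summarised values will have been taken 31 to 42 days after the last dose.
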